# **12 METHODS AND DATA SOURCES**

# 12.1 Methods Summary

- Quantitative Data Collection
  - Two online panel surveys
    - once during pregnancy and once postpartum
    - 30-45 minutes to complete each survey
    - Electronic Health Records
- Qualitative Data Collection (ULCH only)
  - At-home Journal Activity (details in Section 13)
    - Approximately 2 hours effort
      - Completed between survey 1 and survey 2 (with some overlap)
        - a submission reminder is sent with survey 2

# 12.2 Sources of Survey Measures

In order to build the survey, existing measures were used. The questions within the survey measures have been chosen based on their development in either LGBTQIA+ research and/or perinatal research, with special interest in measures that were created using patient involvement. For example, the MADM scale was developed using participatory methods with pregnant patients while the patient experience scale was validated in a sample with both LGBTQIA+ and cisgender heterosexual parents.

# **12.3** Quantitative Data Collection

There are two sources of quantitative data: primary survey data and data from patient records. The online surveys will be used to collect psychosocial data and more detailed demographic data. The second source of data comes from participant's antenatal tests and appointments, along with postnatal data for both parent and infant, both taken from patient records.

#### 12.3.1 Patient Records

The following information collected directly from patient records is being accessed by the study team to diminish stress caused by the study, to ensure clinical consistency, and to reduce recall bias. Data entered by clinical staff into patient records as part of routine antenatal care is then transferred by the study team and paired with the panel survey responses in a secure database via REDCap. Participants will be informed which data from their records will be used by the researchers and provide their consent before any of the information detailed below is accessed for use in the study. No patient health data will be accessed or used without prior consent.

#### 12.3.1.1 Pregnancy Outcomes and Neonatal Health

While documenting birth outcomes and neonatal health, there are a standard set of measures taken right after birth to track growth and development from infancy. These include length/height, weight, head circumference, length of pregnancy (i.e., gestational length), and Apgar score. The latter measure, which is the most complex indicator, is a five domain score that monitors 1) breathing effort, 2) heart rate, 3) muscle tone, 4) reflexes, and 5) skin colour. Each domain can have a value

of 0-2, with an ideal score of 10, with assessment done at 1-minute post birth and 5-minutes postbirth. When additional monitoring is necessary, clinical staff does a third assessment at 10-minutes. Use of standard clinical measures for assessing infant health as indicators for overall outcome follows the efforts to reduce the study's impact while allowing repeatability in a standard clinical setting. With complications during the pregnancy and/or birth, these elements will also come from the patient health records.

#### 12.3.1.2 Demographic Data

To reduce the time and stress placed upon participants, we will draw certain demographic data from patient records rather than asking them to complete additional questions in the survey. Patient age and residential post code will be extracted; with ethnicity both asked and extracted. Post code will be used to determine each participant's "deprivation score"; a composite score that looks at the health of localised areas across England, using weighted scores

a
_ Domain Weight
Income 22.5%
Employment 22.5%
Health & Disability 13.5%
Education, Skills, & Training 13.5%
Crime 9.3%
Barriers to Housing & Services 9.3%
Living Environment 9.3%

for the domains, broken-down in Table 1. The deprivation score will serve as an indicator of vulnerability (included as a structural stressor in Table 3 on page 30), as it represents a community-level measure of resources.

#### 12.3.1.3 Allostatic Load

As there is presently no gold standard for measuring and scoring allostatic load in pregnancy, the proposed analysis (see page 29) takes into consideration the routine clinical tests in antenatal care along with guidance on expanding biomarkers to be more inclusive for racial and ethnic minorities. In order to measure allostatic load (as shown in Table 2), data from four biosystems will assess for overall dysregulation: 1) the cardiovascular system, 2) the metabolic system, 3) the inflammatory system, and 4) the neuroendocrine system. Natural variability within each of the four systems is present as part of foetal development. For analysis, primary indicators for cardiovascular, metabolic, and inflammatory systems, averaged to address the regulatory fluctuations of biosystems within each trimester, will make up the allostatic load index. Including variations in care and site guidelines because of COVID-19. Biomarkers and proxy values are extracted from participant's antenatal records to build a model of allostatic load throughout pregnancy.

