# **14 QUALITATIVE AND QUANTITATIVE ANALYSIS**

# 14.1 Structural Equation Modelling

Using the free data analysis software R and the lavaan package, the quantitative data will be analysed using longitudinal Structural Equation Modelling (SEM). This combines the panel survey data and patient record data within a test of a hypothesized model (Figure 4). This statistical method will allow for the hypothesized roles of resilience and vulnerability to be tested through using the questions that are being asked in the survey instruments. When it is not possible to directly observe concept, latent (i.e., unobservable) variables can become measurable by recording observable components of those concepts. For this study, the observable variables, discussed in the survey instruments sections, define resilience and vulnerability and how these concepts link into the health of the gestational patient, and how they also link into their pregnancy and birth outcomes. These variables are laid out visually in Figure 4 on page 34. The fit of the model will be compared between LGBTQIA+ participants and cisgender heterosexual participants in order to examine inequality in health and their explanatory processes across the two subsamples.

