# **16.2** Sensitive Data and Confidential Advisory Group Review

Because of the methods needed to recruit patients, there is advice being using the contact information that is available in their health records, this project is seeking permission to access this information prior to receiving consent. There will also be confidential and sensitive information that is being requested about biomedical tests that are standard within antenatal care which comprise the variables in the analysis. Aside from contact information and antenatal test results, the rest of the patient information being requested deals with data variables and the ability to link responses to patient records with accuracy.

The identifiers that we will request access to will be for either the purposes of linking patient records and survey responses, or for model building and data analysis. For the linkage of patient records and survey responses, we will need:

- Name (Patient Records)
  - To ensure that the right patient record has been located properly for linking
- Hospital ID no. (Patient Records)
  - For locating and linking infant health records
- Date of Birth (Survey)
  - Used to calculate age, risk, assessing eligibility for study, linking to patient records
- Date of Death (Patient Records)
  - To assess for maternal mortality within the samples
- Geographic identifiers (Survey)
  - The post code for the live and work boroughs collected will be used for assigning the deprivation index value as a structural indicator of vulnerability.

In order to develop the SEM for data analysis, the following identifiers are necessary:

- Date of Birth (parent, Survey)
  - Used for calculating age
- Date of Birth (infant, Patient Records)
  - Used for calculating gestational length
- Date of Death (parent and infant; Patient Records)
  - To assess for infant and parent/maternal mortality within the samples
- Gender (Survey)
  - This is special category data that is necessary because of irregularity in collecting gender as a non-binary variable in-clinic and being a key variable in the research objectives
- Sexual Orientation (Survey)
  - Another variable that is necessary to fulfil the key research objectives
- Ethnicity (Patient Records)
  - Necessary to fulfil the key research objectives to assess for minority stress

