These sensitive data that will be collected, as mentioned above, will be gathered from electronic health records from the gestational patients and their neonates, along with the two surveys and the journal activity. The survey data is gathered online, using REDCAP, while the journal activities are to be completed in a booklet at home. Data from the electronic patient health records will be extracted once per month in order to recruit and build out the sample. For analysis, the variables will go into calculating an allostatic load, which is a score for health and wellbeing. Additional variables are addressed earlier in section 12, this includes both antenatal and postnatal parent data, and requesting access to foetal and neonate health data.

The justification for access to this data is that access to medical records is imperative for this study to succeed. The decision to take this approach was reached in consultation with the clinical staff who serve the patient populations at the centre of this study. In order to link the patient records and data sets, it is necessary to have access to patient identifiable data until the point of analysis. Using factual identifiers is necessary for having at least two points of comparison to make sure that the responses and patient records are properly matched, particularly if respondents register in the study with an email address different from the recruitment email address.

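### Averaging blood pressure within the third trimester lets the timing of birth decide which readings count, which builds a modest artificial link between allostatic load and gestational length

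*Protocol*

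**What the plan says.** Section 12.3.1.3 builds the index from "primary indicators for cardiovascular, metabolic, and inflammatory systems", which are to be "averaged to address the regulatory fluctuations of biosystems within each trimester, will make up the allostatic load index". It gives no trimester boundaries, no common gestational window and no adjustment for the week of measurement. The same section accepts that values move with gestation: "Natural variability within each of the four systems is present as part of foetal development".

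Table 2 (Section 12.3.2.1) lists systolic and diastolic blood pressure as the only cardiovascular indicators, taken at all routine appointments. From 28 weeks on, these fall at 28, 34, 36, 38 and by 41 weeks. Urinalysis, listed under the metabolic system, follows the same schedule. The only caveat is availability under COVID-19 guidance and site differences.

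Section 12.3.1.1 lists "length of pregnancy (i.e., gestational length), and Apgar score" among the birth measures. Section 16.2 requests the infant's date of birth for the structural equation model, "Used for calculating gestational length", and says that "the variables will go into calculating an allostatic load, which is a score for health and wellbeing". Section 14.1 places parent health and birth outcomes in one model and describes "how these concepts link into the health of the gestational patient, and how they also link into their pregnancy and birth outcomes".

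**The concern.** An average over whatever readings exist in a trimester is comparable between people only if they are measured over the same weeks. In the third trimester they are not, because delivery ends antenatal measurement. The number of readings and their average timing are therefore set by gestational length, which is itself an outcome in the model.

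Two things follow. First, if blood pressure drifts over late pregnancy, longer pregnancies get a systematically different average with no difference in health. With a rising trend the artefact is positive: longer gestation, higher apparent load. It would then partly mask any real tendency for higher load to go with earlier birth. Second, early births are averaged over fewer readings, so the measurement error in the index depends on the outcome.

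**Working it through.** The plan gives no figure to reproduce. The check has one part that needs only Table 2 and one part that needs assumptions.

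**Part 1: visits reached before birth (Table 2 only).** Mean week = sum of visit weeks reached ÷ number of visits.

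| Birth | Visits averaged, 28 weeks counted as third trimester | Mean week | Mean week if 28 weeks counts as second trimester |
|---|---|---|---|
| 33 weeks | 28 | 28.0 | no reading |
| 35 weeks | 28, 34 | 62/2 = 31.0 | 34.0 |
| just under 37 | 28, 34, 36 | 98/3 = 32.7 | 70/2 = 35.0 |
| 39 weeks | 28, 34, 36, 38 | 136/4 = 34.0 | 108/3 = 36.0 |
| after the last visit | 28, 34, 36, 38, 41 | 177/5 = 35.4 | 149/4 = 37.25 |

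The last visit is due by 41 weeks rather than at a fixed date, so a birth at about 41 weeks may have four or five readings.

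**Part 2: size (assumed inputs).** Shift in the average = slope per week × difference in mean week. The slope is not in the protocol. Comparing births at 33 and 39 weeks, the difference is 34.0 − 28.0 = 6.0 weeks:
- at 0.3 mmHg per week: 0.3 × 6.0 = 1.8 mmHg
- at 0.6 mmHg per week: 0.6 × 6.0 = 3.6 mmHg

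For the whole sample I simulated blood pressure with no true relation to gestation. The assumptions were 93% of births normal with mean 39.7 and SD 1.2 weeks, 7% with mean 34.5 and SD 2.0, a between-person SD of 8 mmHg and a reading-to-reading SD of 7 mmHg.

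| | 0.3 mmHg/week | 0.6 mmHg/week |
|---|---|---|
| Preterm minus term, 28-week visit included | −1.1 mmHg | −2.2 mmHg |
| Correlation of average with gestational length, 28-week visit included | 0.04 | 0.08 |
| Same correlation, 28-week visit excluded | 0.02 | 0.04 |
| Correlation after week-specific z-scores | about 0 | about 0 |

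With the 28-week visit excluded, about 3% of participants have no third-trimester value at all. A wider set of assumptions (slopes of 0.25 to 1.0 mmHg per week and a distribution with about 18% preterm births) gave correlations of 0.03 to 0.14. At zero slope the correlation vanishes.

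**Whole index.** Suppose the three systems carry equal weight, are standardised and independent, and only blood pressure is affected. The correlation is then divided by √3 = 1.73: 0.04/1.73 = 0.02 and 0.08/1.73 = 0.05. Urinalysis shares the visit schedule and could add to this if it is one of the primary indicators, which the protocol does not say.

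**Noise.** SD of an average of k readings = √(8² + 7²/k). One reading gives √113 = 10.6 mmHg and four readings give √76.25 = 8.7 mmHg, whatever the slope.

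**The case against.** The strongest objection is that the protocol nowhere states a path from allostatic load to gestational length. Its questions concern what vulnerability and resilience do to parent health and to neonates, and load can be read as the parent-health outcome. This stands: a reader might infer that load is meant to explain gestational length, but the text does not say so and the model diagram could not be read. It does not remove the point, because two parallel outcomes in one model also acquire the artificial association.

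A second objection is that the averaging rule leaves room for standardising readings first, and that scoring detail can sit in an analysis plan. It is true that standardisation is compatible with the sentence. But the rule that is fixed, averaging within trimester, produces the artefact unless week of measurement is dealt with, so this is more than missing detail.

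Third, size. It is tempting to set the preterm-versus-term difference, about 0.13 to 0.25 SD of the averaged value, beside the planning effect size of 0.3 in Section 8.2.3.2. The documents do not support that comparison. The 0.3 comes from a sample-size calculator for structural equation models, whereas the other figure contrasts a small preterm subgroup with everyone else. The whole-sample correlation is the nearer comparator, and it is modest.

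Fourth, the comparison of model fit between the two groups is shifted only if gestational length differs between them, which nothing here shows. That stands as a limit on the harm. Finally, the sparser schedules of BMI, glycated haemoglobin and white cell count add little, since an average of one reading is simply that reading.

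**Conclusion.** The point holds as a modest, avoidable artefact. That the readings averaged depend on when birth occurs follows from Section 12.3.1.3 and Table 2 alone. That this matters for the analysis follows from gestational length being an outcome in the same model. Bias in the mean also requires blood pressure to change over late pregnancy. The protocol says values vary with foetal development but gives no size.

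Under the assumed rise of 0.3 to 0.6 mmHg per week, the spurious correlation for averaged blood pressure is about 0.02 to 0.08. The lower part of that range applies if the 28-week visit belongs to the second trimester. For the whole index it is smaller still under the equal-weight assumption. The greater noise in early births' averages does not depend on the slope. The plan should be corrected, but this does not threaten the study's main comparison.

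**What to change.** In Section 12.3.1.3, state where each trimester begins and ends. Specify that each repeated reading is expressed as a z-score for its gestational week, using the study's own readings, and that the z-scores are then averaged within trimester. In the simulation this removed the spurious correlation.

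Standardising does not equalise the number of readings, so early births keep noisier averages. As a sensitivity analysis only, repeat the birth-outcome analysis with readings from a common gestational window. For births after 34 weeks, for example, the 28- and 34-week visits give a mean week of 31.0 for everyone and no timing shift at any slope. Making such a window the main analysis would discard late readings and cut against the aim of modelling load throughout pregnancy, so I would not go that far.

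The cost is a short addition to the protocol and a little extra programming. No new data are needed.

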# 12.3.2 Longitudinal Panel Survey

Using existing, validated scales, identical panel surveys will assess for differences in resilience and vulnerability scores in pregnancy (survey 1) and postpartum (survey 2). The Research Electronic Data Capture (REDCap) survey platform (see appendix 13) will collect data securely, allowing survey responses to be stored directly onto a digitally secure remote server that will be accessed by the study team (i.e., the Data Safe Haven—see appendix 14). Data extracted from patient records will be linked to participants survey responses after participation via data entry forms in the secure REDCap platform.

#### 12.3.2.1 Allostatic Load

The Edinburgh Postnatal Depression Scale (EPDS) is part of the longitudinal panel surveys, as mentioned in Table 2. This scale, developed and validated ( $\alpha$ =0.87) in Scotland, is widely used in the UK with parents during pregnancy and postpartum.

Biosystem	Antenatal Test	Collection Points
Cardiovascular system	Systolic blood pressure	All routine
		appointments*
		
 
Initial appointment
 

		• At 16 weeks
		• By 22 weeks
		• At 28 weeks
		• At 34 weeks
		• At 36 weeks
		• At 38 weeks
		• By 41 weeks
	Diastolic blood pressure	All routine
		appointments*
Metabolic system	Body mass index	Pre-pregnancy
		By 41 Weeks
	Glycated haemoglobin	First trimester
		Second trimester*
		Third trimester
	Urinalysis (dip and/or microscopy)	All routine
		appointments*
Inflammatory system	White blood cells count	First trimester
		Second trimester*
		Third trimester
Neuroendocrine system	Edinburgh Postnatal Depression Scale	Panel Survey 1
	(EPDS)	Panel Survey 2
	Fundal height	All routine
	-	appointments*

Table 2: Parent Allostatic Load Biomarkers and Proxies

\*when available because of COVID-19 guidance and potential differences in site implementation

#### 12.3.2.2 Vulnerability: Measures

Scales used to assess vulnerabilities are listed in Table 3, and the details of the variables (grouped by indicator and/or construct) are laid out in appendix 15. The included scales were selected because of their ability to measure both proximal (intrapersonal) and distal (interpersonal) minority stressors, along with more general measures of stress (e.g., household and community level resources) to allow for the additive nature of minority stress to be assessed. Most of the scales were validated in LGBTQIA+ led and focused projects, which was a point of importance in the development of this study.

Scale	Source of Variables and Methods	Latent Variable
Level of Outness*	Meyer, Rossano, Ellis, & Bradford 	Intrapersonal stressor
Felt Stigma	Herek, GM 	Intrapersonal stressor
Homelessness/Child Welfare	Harris & Udry  , adapted by Meyer, et al. 	Interpersonal stressor
Police Interactions*	English, Bowleg, Rio-Gonzalez, Tschann, Angans, & Malebranche  , amended by Meyer, et al. 	Interpersonal stressor
Stressful Life Events	National Institutes of Health 	Interpersonal stressor
Everyday Discrimination	Williams, Yu, Jackson, & Anderson  , adapted by Meyer, et al. 	Interpersonal stressor
Chronic Strains	Wheaton  , abridged by Meyer, et al. 	Interpersonal stressor
Household Vulnerability Index*	Flanagan, Gregory, Hallisey, Heitgerd, & Lewis 	Structural stressor
Deprivation Score	Ministry of Housing, Communities, & Local Government 	Structural stressor

Table 3: Sources for the Vulnerability Indicators

\*Adapted or further adapted for this study

Table 4: Sources for Resilience Indicators

Scale		Latent Variable
Coping*	Carver, Weintraub, & Scheier  , Carver 	Intrapersonal resilience
Perceived Social Support	Zimet, Dahlem, Zimet, & Farley 	Intrapersonal resilience
Patient Experience Scales* (comfort, trust, safety, support)	[name] 	Interpersonal resilience
Shared Decision-making (competence, control, communication)	Vedam, Stoll, Martin, Rubashkin, Partridge, Thordarson, & Jolicoeur 	Interpersonal resilience
Emotional Reactivity	Jimenez-Torres, et al. 	Interpersonal resilience
Community Connectedness*	[name] & Meyer 	Sociopolitical resilience
Civic engagement	Porter  & Pancer,  adapted by Meyer, et al. 	Sociopolitical resilience

\*Adapted or further adapted for this study

#### 12.3.2.3 Resilience: Measures

Scales used to assess resilience are predominantly from ante- and perinatal research studies. An exception to this is the emotional reactivity scale, which was validated in HIV+ Latin women. The only scale validated in a study on LGBTQIA+ pregnancy is the Patient Experience scale. Along with the further details in Table 4, these measures are laid out in appendix 15.

# **12.4 Inclusion of Neonate Patient Data**

Data on infant(s) health in the neonatal period, immediately following birth, will be obtained from electronic medical records. This is to allow access to birth outcomes data.

Gestational patients who are taking part in the study, who were recruited during their pregnancy, will be asked to provide the details necessary to link infant patient records with their parent's survey responses. The consenting process of the gestational patient will include that this need for and use of foetal and infant health data will be part of the collection process. The consenting processes and patient information sheets will be given only to the gestational patients who are taking part in the study. As the neonates would be too young to give consent and the consent necessary is only to health records and not for any care, clinical visits, or any other face-to-face activities, the study requires only the access to information request and consent from the parents.

